10.5 Discontinued Subjects

10.5.1 Screen Failures

Screen failures are subjects who were excluded from the study after signing the informed consent and prior to administering treatment.

The Investigator must document the reason for screen failure in the subject's case history source documents.

Subject numbers must not be re-used.

Do cum ent: TDOC-0054099 **Version:** 2. 0; Most - Recent; Effective; CURRENT

St atu s: Effective Page 50 of 71

10.5.2 Discontinuations

Discontinued subjects are individuals who voluntarily withdraw or are withdrawn from the study by the Investigator after informed consent is signed and before the last visit is completed.

Subject numbers of discontinued subjects must not be re-used.

Subjects may discontinue from study or study treatment at any time for any reason. Subjects may also be discontinued from study treatment at any time if, in the opinion of the Investigator, continued treatment poses a lisk to their health.

If a subject discontinues from study treatment, evely effoll must be made to keep the subject in the study and to continue with the study assessments as specified in the schedule of study procedures and assessments until the final visit.

For subjects discontinuing from the study, the Investigator must complete all Exit procedures according to Table 3-1 Schedule of Study Procedures and Assessments and Section 10.4.3, if the subject is willing and able, and if in the opinion of the Investigator it is safe for the subject to do so.

The Investigator must document the reason for study or treatment discontinuation in the subject 's case hist01y so urce documents.

To ensure the safety of all subjects who discontinueearly, Investigatorsmust assess each subject and, if necessaly, advise them of any therapies and/or medical procedures that may be needed to maintain their health.

10.5.3 Schedule of Procedures and Assessments for Subjects Discontinued from Investigational Product

In the case of subjects who discontinue IP but do not discontinue from the study, subjects must be assessed with below tests till the end of study, if applicable.

Effectiveness assessment (photopic light conditions)	Safety assessment
 Distance VA (4 m), Monocular (1st and/or 2nd eye) UCDVA Binocular UCDVA 	Adverse Device Events including Secondaly Surgical Intellections (SSis) related to the optical propelties of the IOL

Do cum ent: TDOC-0054099 **Version:** 2. 0; Most-Recent; Effective; CURRENT

St atu s: Effective Page 51 of71

Binocular BCDVA	
Inte1mediate VA (60 cm)	Device Deficienc ies
• Monocular (1st and/or 2d d eye) UCIVA	
Binocular UCIVA	
Near VA (40 cm)	Fundus Visualization
• Monocular (1 st and/or 2 nd eye) UCNVA	Fundus Examination
Binocular UCNVA	
Photopic binocular defocus cmve	Intraocular Pressure
Photopic best conected binocular contrast sensitivity	Surgical problems
with & withoutglare	
Subjective symptoms	Subjective Posterior Capsule
	Opacification
	Posterior Capsulotomy
	Lens decentration and tilt

Depending on the circumstance, the subject may continue in the study or may be discontinued as outlined as below.

Eye	Conditions	Status/Follow-up
	 Exclusion during surgely Lens does not touch eye	Subject discontinued
1 st Operative Eye	Exclusion during surgely	 Subject continued 1st eye:
	Lens touches eyeLens is not implanted	No effectiveness assessments conducted
		0 Monocular safety

Page **52 of 71**

Do cum ent: TDOC-0054099

St atu s: Effective

Version: 2. o; Most-Recent; Effective; CURRENT

St atu S: Effective	1	rage 52 01 /1
		 assessments conducted at postoperative visits 2nd eye: Not implanted
	 Exclusion during surgely Lens implanted 	 Subject continued 1st eye: Monocular and binocula r effectiveness assessments conducted at postoperative visits Safe ty assessments conducted at postoperative visits 2nd eye: Proceed to implant study lens as scheduled
2 nd Ope rative Eye	 Exclusion during surgely Lens does nottouch eye 	Subject continued 1st eye: 0 Monocular effectiveness assessments perf01med at postoperative visits 0 Safety assessments perf01med at postopera tive visits 2nd eye: 0 No effectiveness assessments conducted Rep01tAEs and Device Deficiencies, if any
Eye	Conditions	Status
2 nd0 _{per atlve} Eye	Exclu sion during surgely	 Subject continued 1st eye:

Do cum ent: TDOC-0054099 Version: 2. 0; Most-Recent; Effective; CURRENT

St atu s: Effective Page 53 of71

St atu S. Effective		rage 33 017
•	Lens touches eye Lens not implanted	 Monocular effectiveness assessments performed at postoperative visits
		o Monocular safety assessments performed at postoperative visits
		• 2 nd eye:
		No effectiveness assessments conducted
		o Monocular safety assessments performed at postoperative visits
•	Exclusion during surgely	 Subject continued 1st eye:
•	Lens implanted	o Monocular and binocular effectiveness assessments conducted at postoperative visits
		O Safety assessments conducted at postoperative visits
		• 2 nd eye:
		 Monocular and binocular effectiveness assessments conducted at postoperative visits
		Safety assessmentsconducted at postoperativevisits

Do cum ent: TDOC-0054099 **Version:** 2. 0; Most-Recent; Effective; CURRENT

St atu s: Effective Page 54 of 71

10.6 Clinic al Study Termina tion

The Study Sponsor reserves the right to close the investigational site or ternlinate the study in its entirety at any time.

If the clinical study is prematurely terminated or suspendedby the Study Sponsor:

- The Study Sponsor must:
 - o Immediately notify the Investigator(s) and subsequently provide instructions for study termination.
 - o Info1mthe Investigator and the regulat01y au thorities of the te1mination/suspension and the reason(s) for the te1mination/suspension.
- The Investigator must:
 - o Promptly notify the IRB/IEC of the termination or suspension and of the reasons.
 - o Provide subjects with recommendations for post-study treatment options as needed.

The Investigator may te1mi nate the site's prut icipation in the study for reasonable cause.

10.6.1 Follow-up of subjects after study participation has ended

Following this study, the subject will return to their eye care professional for their routine eye care.

11 ADVERSE EVENTS AND DEVICEDEFICIENCIES

11.1 General Information

An AE is any untoward medical occmTence, umntended disease or injmy, or untoward clinical signs (including abn01mal labora t01y findings) in subjects, users, or other persons, whether or not related to the investigational medical device (test alticle). Refer to the Glossaiy of Telms for categories of AEs and SAEs.

Do cum ent: TDOC-0054099 Version: 2. 0; Most-Recent; Effective; CURRENT

St atu s: Effective Page 55 of 71

Figure 11-1 Categorization of All Adverse Events

[figure not shown]
[figure not shown]

Figure 11-2 Categorization of All Serious Adverse Events

In addition to rep01ting all AEs (serious and non-serious) meeting the definitions, the Investigator must rep01t any occunence of the following as an SAE:

Cumulative Serious Adverse Events

Cystoid macular edema

Do cum ent: TDOC-0054099

Version: 2. o; Most-Recent; Effective; CURRENT

Page 56 of 71

Hypopyon

St atu s: Effective

- Endophtalmitis
- Lens dislocation
- Pupillaiy block
- Retinal detachment
- Secondary surgical intervention (excluding posterior capsulotomy)

PersistentSerious Adverse Events

- · Corneal strom al edema
- Cystoid macular edema
- Iritis
- Raised IOP requiring treatment

This list is consistent with the categories provided in EN ISO 11979-7:2014. A persistent AE is an AE that is present at the conclusion of a clinical investigation per EN ISO 11979-1:2012. Any other potentially sight-threatening event may also be considered serious based upon the judgment of the Investigator and should be report ed appropriately as delineated in Section 11.3.

Device Deficiencies

A device deficiency may or may not be associated with subject ha1m (ie, ADE or SADE); however, not all ADEs or SADEs are due to a device deficiency. The Investigator should determine the applicable category for the identified or suspect device deficiency and report any subject haim separately.

- Failure to meet product specifications (eg, incolTect IOL power)
- IOL defect
- Broken IOL optic
- Broken IOL haptic
- Scratched IOL optic
- Unsealed device packaging
- Suspect product contamination (IOL)

Do cum ent: TDOC-0054099 **Version:** 2. 0; Most-Recent; Effective; CURRENT

St atu s: Effective Page 57 of 71

11.2 Monitoring for Adverse Events

At each visit, after the subject has had the oppoltunity to spontaneously mention any problems, the Investigator should inquire about AEs by asking the standard questions:

- "Have you had any health problems since yom last study visit?"
- "Have there been any changes in the medicines you take since your last study visit?"

Changes in any protocol-specific parameters and/or questionnaires evaluated during the study are to be reviewed by the Investigator. Any untoward (unfavorable and unintended) change in a protocol-specific parameter or questionnaire response that is clinically relevant, in the opinion of the Investigator, is to be rep01ied as an AE. These clinically relevant changes will be rep01ied regardless of causality.

11.3 Procedures for Recording and Reporting

AEs are collected from the time of inf01med consent. Any pre-existing medical conditions or sign s/symptoms present in a subject prior to the stali of the study (ie, before info1med consent is signed) are not considered AEs in the study and should be recorded in the Medical Hist01y sect ion of the eCRF.

In addition, aqueous cells and flare, corneal edema, raised IOP, and superficial punctate keratitis are examples of early postoperative findings that are typically observed following ocular surgery. The se are not considered AEs if they can be reasonably expected to resolve within a week and not result in any untoward long telm visual outcome impact.

For each recorded event, the ADEs and SAEs documentation must include: date of occmTence, seve rity, treatment (if applicable), outcome, and assessments of the seriousness and causality. In addition, the Investigator must document all device deficiencies reported or observed with test allicles on the Device Deficiency eCRF. The site must submit all available information on ADEs, SAEs, and device deficiencies to the Study Sponsor immediately as follows:

- All SAEs must be repolied immediately (within 24 homs) of the Investigator's or site's awareness.
- ADEs that do not meet seriousness criteria and device deficiencies must be reported within 10 calendar days of the Investigator's or site's awareness.
- A printed copy of the completed Serious Adverse Event and Adverse Device Effect and/or Device Deficiency eCRF must be included with product retmns.

Do cum ent: TDOC-0054099 **Version:** 2. 0; Most-Recent; Effective; CURRENT

St atu s: Effective Page 58 of 71

 Additional relevant information after initial reporting must be enteredinto the eCRF as soon as the data become available.

- Document any changes to concomitant medications on the appropriate eCRF.
- Document all relevant info1mation from Discharge Summa1yAutopsy Rep01t, Ce1tificate
 of Death etc, if applicable, in nan ative section of the Adverse Device Effect (for related
 AEs) and Serious Adverse Event eCRF.

Note: Should the EDC system become non-operational, the site must complete the appropriate paper Serious Adverse Event and Adverse Device Effect and/or Device Deficiency F01m. The completedform is faxed or emailed to the Study Sponsor (Korean Novaltis Patient Safety Desk) at or is faxed at or according to the timelines outlined above; however, the rep01ted inf01mation must be entered into the EDC system once it becomes operational.

Any AEs and device deficiencies for non-study marketed devices/products (ie, but not limited to BSS, OVD, Delive1ysystems, Phacoemulsification systems, VAhandpieces) will be considered and processed as spontaneous (following the postmarket vigilance procedures) and should be communicated to the device's/product's manufacturer as per local requirements.

Study Sponsor representatives may be contacted for any protocol related question and their contact info1mation is provided in the Manual of Procedures (MOP) that accompanies this protocol.

Frnther, dependin g upon the nature of the AE or device deficiency being reported, the Study Sponsor may request copies of applicable p01tions of the subject's medical records. The Investigator must also repo1t all AEs and device deficiencies that could have led to a SADE according to the requirements of regulat01y authorities or IRB/IEC.

Intensity and Causality Assessments

Where appropriate, the Investigator must assess the intensity (severity) of the AE based upon medical judgment with consideration of any subjective symptom(s), as defined below:

Intensity (Severity)

Mild: An AE is mild if the subject is aware of but can easily tolerate the sign or symptom.

Moderate: An AE is moderate if the sign or symptom results in discomfort significant enough to cause interference with the subject's usual activities.

Document: TDOC-0054099 **Version:** 2.0; Most-Recent; Effective; CURRENT

Status: Effective Page 59 of 71

Severe: An AE is severe if the sign or symptom is incapacitating and results in the subject's inability to work or engage in their usual activities.

For every AE in the study, the Investigator must assess the causality (Related or Not Related to the medical device or study procedure). An assessment of causality will also be performed by Study Sponsor utilizing the same definitions, as shown below:

Causality

1. Definitely related

Event which has definitive time relationship to the use of the device of interest, cannot be explained by other reasons but the device of interest, has symptom disappearance to discontinuation of the device of interest and reappears when the device of interest is rechallenged (only when rechallenge is possible to do so).

Also event is consistent to already known information of the device of interest or other devices of the same class.

2. Probably related

Event where there is evidence that the device of interest was used, has reasonable time relationship to the use of device of interest, can be explained mainly by the device of interest rather than other reasons, and has symptom disappearance to discontinuation of the device of interest.

3. Possibly related

Event where there is evidence that the device of interest was used has plausible time relationship to the use of device of interest, device of interest and other reasons have similar chances of resulting to an event, has symptom disappearance to discontinuation of the device of interest.

4. Possibly not related

Event where there is evidence that the device of interest was used, can be reasonably explained by other reasons, has symptom disappearance or there is uncertainty of the symptom when device of interest is discontinued has no symptom reappearance or there is uncertainty of the symptom when device of interest is rechallenged (only when rechallenge is possible to do so).

5. Definitely not related

Event where device of interest was not used has no reasonable time relationship to the use of device of interest, can be explained by other reasons.

Document: TDOC-0054099 **Version:** 2.0; Most-Recent; Effective; CURRENT

Status: Effective Page 60 of 71

6. Unknown

Cannot be judged because information is insufficient or contradictory and cannot be supplemented or confirmed.

*Assessment criteria used in reporting to Novartis Patient Safety based upon the 6 classifications

Safety Reporting Form	MFDS Guideline
Suspected	Definitely related, Probably related, Possibly related, Unknown
Not suspected	Possibly not related, Definitely not related

The Study Sponsor will assess the AEs and may upgrade the Investigator's assessment of seriousness and/or causality. The Study Sponsor will notify the Investigator of any AEs that are upgraded from non-serious to serious or from unrelated to related.

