The ACRYSOF IQ PanOptix Presbyopia Correcting IOL, Model TFNT00 is a multifocal lens intended to provide optical performance and spectacle independence similar to the ACRYSOF IQ RESTOR +3.0 D Multifocal IOL (Model SN6AD1) at near (40 cm) and distance, with the additional benefit of intermediate vision at 60 cm.

After CE mark approval in EU, a postmarket clinical investigation of the ACRYSOF IQ PanOptix Presbyopia Correcting IOL, Model TFNT00 was conducted at 14 clinical sites in regions where the ACRYSOF IQ PanOptix Presbyopia Correcting IOL, Model TFNT00 is approved for commercial distribution (Australia, Belgium, Chile, France, Germany, Italy, Netherlands, Spain, and the United Kingdom). This study was a prospective, single arm, unmasked, non-randomized, multi-center study. The objective was to describe visual outcomes and confirm long-term safety and performance at 12 months (330-420 days) post bilateral implantation of the ACRYSOF IQ PanOptix Presbyopia Correcting IOL, Model TFNT00. The 6-month interim analysis results showed that the ACRYSOF IQ PanOptix Presbyopia Correcting IOL, Model TFNT00could provide simultaneous visual performance for near, intermediate, and distance with a mean VA of 20/20 for distance and a mean VA of 20/25 for intermediate and near vision. The ACRYSOF IQ PanOptix Presbyopia Correcting IOL, Model TFNT00 is safe when implanted according to the approved label.

Based upon the formal risk assessment, the ACRYSOF IQ PanOptix Presbyopia Correcting IOL, Model TFNT00 demonstrates a favorable risk profile that is comparable to previously approved ACRYSOF multifocal IOLs. The ACRYSOF IQ PanOptix Presbyopia Correcting IOL, Model TFNT00 is designed to provide the benefit of increased intermediate vision while maintaining visual performance at near and distance. Potential risks following implantation of ACRYSOF IQ PanOptix Presbyopia Correcting IOL include visual

Document: TDOC-0054099 Version: 2.0; Most-Recent; Effective; CURRENT

Status: Effective Page 30 of 71

disturbances such as glare and halos, which are known risks for multifocal IOLs. The benefits of improved intermediate vision, when weighed against the risks of visual disturbances, result in a benefit to risk profile that is favorable for the ACRYSOF IQ PanOptix Presbyopia Correcting IOL, Model TFNT00.

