5.3 Statistical Methods for Safety Analyses

The analysis set for safety analyses is the safety analysis set as defined in Section 2.2. Baseline will be defined as the last measurement prior to exposure to the test product.

5.3.1 Adverse Events (Including Secondary Surgical Interventions Related to the Optical Properties of the IOL)

The definition of an Adverse Event (AE) and an Adverse Device Effect is as set forth in section 1 of the study protocol.

Counts and percentage of eyes with ocular adverse events, including the SSI will be presented by first, second operative eyes and overall. Counts and percentages of subjects with non-ocular adverse events will be presented by subject. Incidence by visit and cumulative incidence will be presented.

AEs will be summarized using the following tables:

- All Adverse Events (Serious and Non-Serious Combined)
 - Ocular
 - Non-Ocular
- o All Adverse Device Effects (including Serious Adverse Device Effects)
 - Ocular
 - Non-Ocular
- All Serious Adverse Events (including Serious Adverse Device Effects)
 - Ocular
 - Non-Ocular
- Subject listings
 - Ocular Serious Adverse Events
 - Non-Ocular Serious Adverse Events
 - Ocular Non-serious Adverse Events
 - Non-Ocular Non-serious Adverse Events
 - Adverse events resulting in study discontinuation
 - Adverse events resulting in death

Additionally, any adverse event experienced by a subject during the screening period will be presented separately in a listing.

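### Read literally, no related causality grade can be met while the lens stays in the eye, and the plan does not say how Unknown enters the adverse device effect tables.

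*Protocol*

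**What the plan says.** Protocol Section 11.3 first asks for a two-way judgement: "the Investigator must assess the causality (Related or Not Related to the medical device or study procedure". It then defines six grades.

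- *Definitely related*: the event "cannot be explained by other reasons but the device of interest, has symptom disappearance to discontinuation of the device of interest", and it "reappears when the device of interest is rechallenged (only when rechallenge is possible to do so".
- *Probably related*: the event is explained mainly by the device "rather than other reasons, and has symptom disappearance to discontinuation of the device of interest".
- *Possibly related*: the device and "other reasons have similar chances of resulting to an event, has symptom disappearance to discontinuation of the device of interest".
- *Possibly not related*: other reasons can reasonably explain the event, and it "has symptom disappearance or there is uncertainty of the symptom when device of interest is discontinued".
- *Definitely not related*: described in terms of the device not being used, no reasonable timing, and an explanation by other causes.
- *Unknown*: the information is too thin or contradictory to judge and cannot be improved.

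A small table in the same section, for reporting to the safety desk, places the three related grades and *Unknown* under Suspected. *Possibly not related* and *Definitely not related* go under Not suspected. The sponsor also assesses causality, with the same definitions, and may upgrade the investigator's grade.

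Protocol Table 9-1 describes the lens as an implant meant to stay for the subject's lifetime. Protocol Section 5.3 mentions replacement or explantation only for some cases, and names as risks visual "disturbances such as glare and halos, which are known risks for multifocal IOLs".

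Relatedness is used in three places: the adverse event summary by relationship (Protocol Section 12.6), the SAP 5.3.1 table headed "All Adverse Device Effects (including Serious Adverse Device Effects", and the 10-calendar-day reporting limit for non-serious adverse device effects (Protocol Section 11.3).

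**The concern.** A scale that relies on withdrawal of the product suits a drug. Here the product remains in the eye unless it is explanted or exchanged, so for most eyes the withdrawal criterion will never be observable. The protocol recognises this kind of difficulty for rechallenge and excuses it where it is not feasible, but gives no such allowance for discontinuation.

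What is at stake is the attribution of events to the lens. The study has a single arm and no control, so there is no comparison group against which to read event rates, and the causality grade is the main planned way to separate lens effects from the rest. If sites apply the definitions literally, some events that the scale intends as possibly related will be graded the other way. If some sites apply them literally and others use common sense, the grades will not be comparable between sites.

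**Working it through.** No arithmetic applies, and the plan states no figure on this point. The check is to follow an event through the six definitions when the lens is still in the eye.

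1. **Related grades.** *Definitely*, *Probably* and *Possibly related* each carry the discontinuation clause. The feasibility qualifier in *Definitely related* is attached to rechallenge alone. With the lens retained, 0 of the 3 grades can be met. This includes an event that fades by itself with the lens in place, since that is not disappearance on discontinuation.

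2. **Definitely not related.** This does not fit an event that follows implantation with plausible timing.

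3. **Competing explanation present.** *Possibly not related* is open. It needs a reasonable alternative cause and accepts uncertainty about what happens on discontinuation. (I take that uncertainty to cover a lens that was never removed. If it does not, the event goes to *Unknown*.) Similar chances for the device and another cause is the protocol's own test for *Possibly related*. Such an event therefore moves from *Possibly related* to *Possibly not related*, and from Suspected to Not suspected, solely because the lens was not taken out.

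4. **No competing explanation.** A persistent halo with no other cause fails *Possibly not related*, which needs that other cause. Only *Unknown* is left, and the safety desk table counts it as Suspected.

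5. **From six grades to two.** Section 11.3 asks for Related or Not Related, while Section 12.6 and SAP 5.3.1 tabulate by relationship and by adverse device effect. SAP 5.3.1 takes the definition of an adverse device effect from Protocol Section 1, which rests on relatedness to use of the device. The only mapping given is the safety desk's Suspected / Not suspected split. Nothing says that it also governs the tables.

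The effect on a table can be written without assumed figures. Let *e* be the events where the lens was removed and the symptom then disappeared. Let *a* be the retained-lens events with no other explanation. Let *b* be the retained-lens events with a competing explanation that would meet a related grade but for the discontinuation clause. The count of related events is then:

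- literal reading, *Unknown* counted as not related: *e*
- literal reading, *Unknown* counted as related: *e + a*
- discontinuation clause conditional on removal, no competing-cause events misgraded: *e + a + b*

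So *b* is lost whichever way *Unknown* is treated, and *a* depends on a choice that neither document makes. The documents give no values for *a*, *b* or *e*.

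**The case against.** Three stronger readings are tempting, and the documents do not support them.

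- A reader might infer that the device-related rate is biased toward zero, or that halos and glare cannot count as device effects unless the lens comes out. That follows only if *Unknown* is treated as not related, and no section says so. The one mapping in the protocol puts *Unknown* with the related grades. The adverse device effect definition in Protocol Section 1 does not itself refer to the six-level scale.
- A reader might infer that a purely surgical event has no grade. It does: with the device used and another reasonable cause present, *Possibly not related* fits. What remains is narrower. Section 11.3 asks about the device or the study procedure, but the definitions speak only of the device, so relatedness to the procedure is not graded separately.
- A reader might infer that the information is lost. SAP 5.3.1 tabulates all ocular and non-ocular events whatever their causality. Serious events are reported within 24 hours regardless of causality. Surgical re-interventions attributed to the lens optics have their own table (SAP 5.3.2). Subjective symptoms are a secondary endpoint.

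It can also be said that the sponsor may upgrade a grade. That helps only in part, because the sponsor must use the same definitions and so meets the same clause. Finally, the safety desk table heads the six levels as an MFDS guideline. Whether the sponsor is free to reword them cannot be told from the documents, so the remedy should not depend on rewording.

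These objections limit the consequence. They do not remove the clause or supply the missing mapping.

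**Conclusion.** The point stands in a limited form. As written, no related grade can be met for a retained lens. Events with a competing cause can move from *Possibly related* to *Possibly not related*, and so out of Suspected. Events with no other cause become *Unknown*, whose place in the relationship summary and the adverse device effect tables is undefined. The same uncertainty reaches the 10-day reporting limit for non-serious adverse device effects.

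This rests on a literal reading of Section 11.3, on discontinuation of an implant meaning its removal, and on uncertainty in *Possibly not related* covering a lens left in place. Sites may read the definitions more sensibly, in which case the defect is inconsistency between sites. The size cannot be stated as a rate.

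I would rate it as a clarification that should be made, not as essential. The study is descriptive with no hypothesis tests, all adverse events are tabulated regardless of causality, and neither the primary endpoint nor the sample size is affected.

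**What to change.** 1. In Protocol Section 11.3, make the discontinuation clause in the three related grades conditional, as rechallenge already is: it applies only if the lens was explanted or exchanged. If the MFDS wording must stay, add an interpretive note to the same effect.
2. State in the protocol and in SAP 5.3.1 that the existing Suspected / Not suspected split, with *Unknown* counted as Suspected, defines Related / Not Related for the relationship summary and the adverse device effect tables.
3. Say whether relatedness to the study procedure is to be recorded separately from relatedness to the device.

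The cost is a clause or note in the protocol and one sentence in each document, plus an eCRF item if procedure relatedness is recorded separately. The reported adverse device effect rate may become slightly less favourable. No visit, assessment or sample size changes.
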